## 8.4.4 Clinical Laboratory Testing

A Clinical Laboratory Improvement Amendments (CLIA) certified [either central or local] laboratory will perform the clinical laboratory tests for this study as scheduled in Table 8-1. Tests are listed in Table 8-2 and will be performed at Screening, at each Safety Assessment Visit, at Unscheduled Visits and at the EOS; for subjects with excised lesions on both the face and the body, clinical laboratory samples will be collected only at the second EOS visit (i.e, at the EOS for Body).

Table 8-1 Clinical Laboratory Tests

Clinical Laboratory Tests	
Hematology:	Serum Chemistry:
Red Blood Cell Count (RBC)	Blood Urea Nitrogen (BUN)
White Blood Cell Count (WBC) w/ differential (absolute)	Creatinine
Hematocrit	SGOT (AST)
Hemoglobin	SGPT (ALT)
Mean Corpuscular Volume (MCV)	Lactic Dehydrogenase (LDH)
Mean Corpuscular Hemoglobin Concentration (MCHC)	Alkaline Phosphatase (ALP)
Platelet Count	Total Bilirubin
	Total Protein
	Albumin
	Glucose
	Calcium
	Sodium
	Chloride
	Potassium
	Bicarbonate
Pregnancy Test: (Only on subjects of childbearing potential)	Serum tryptase
Serum β-hCG (Screening, Safety Assessment Visits, and EOS)	
Urine (prior to injection on Day 1 of each week)	
T-Cell Clonality (Central lab only)	Expansion Cohorts 4 and 5
	Serum Pharmacokinetics (PK) [Central lab only]

EOS=end of study (visit); EOT=end of treatment (visit)

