## 5.2. Inferential and Descriptive Statistics

No formal inferential statistical analyses will be performed. Descriptive statistics for continuous variables will include number of subjects, mean, standard deviation, median, minimum, and maximum. Counts and percentages will be provided for categorical/ordinal variables. Unless specified in a display footnote, denominators for percentages will only consider the number of subjects being summarized or the number of non-missing responses being summarized, as appropriate. Conversion factors that may be used are as follows: 1 C = 33.8 F; 1 in = 2.54 cm; 1 kg = 2.2 lb; 1 month = 30.4375 days; 1 year = 365.25 days. The number of decimal places shown in displays will follow as closely as possible the below convention:

Statistic	Decimal Places *
n	0
Mean	1 more than Min, Max
Standard Deviation	2 more than Min, Max
Median	1 more than Min, Max
Min, Max	Same as most common in data
Percent	1

\* May be limited to less than stated as space provides

Tables will be summarized for scheduled visits unless stated otherwise in this SAP, and listings will be provided for data collected via the electronic data capture (EDC) system and from external vendor(s). If date of assessment, collection, measurement, and the like is not available, then date of visit will be used if available, where applicable. If there are multiple readings taken per visit, the most recent reading from that visit will be used in summaries, unless there are pre-dose and post-dose readings taken at the same visit, as mentioned elsewhere in this SAP.

The analyses described in this plan are considered *a priori*, in that they have been defined prior to database lock. Any analysis added after the database lock will be considered post hoc and exploratory. Post hoc analyses will be labeled as such on the displays.

Verrica Pharmaceuticals Inc.  
Protocol: VP-315-201

Statistical Analysis Plan  
6-Sep-2024

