## 9.2. Clinical Laboratories

Summaries of (a) serum chemistry, (b) hematology, and (c) serum tryptase will be provided using descriptive statistics and the safety population. Any clinically significant post-baseline laboratory result is to be collected as an adverse event and included in the summary of adverse events.

Verrica Pharmaceuticals Inc.  
Protocol: VP-315-201

Statistical Analysis Plan  
6-Sep-2024

Results for serum tryptase and for the following laboratory parameters are expected to be available for summarization using the International System of Units (i.e., standard units).

Serum Chemistry	Hematology

 
• Albumin
 
• Alkaline Phosphatase (ALP)
 
• Alanine Aminotransferase (ALT) (Serum Glutamic Pyruvic Transaminase (SGPT))
 
• Aspartate Aminotransferase (AST) (Serum Glutamic Oxaloacetic Transaminase (SGOT))
 
• Blood Urea Nitrogen (BUN)
 
• Bicarbonate
 
• Calcium
 
• Chloride
 
• Creatinine
 
• Glucose
 
• Lactic Dehydrogenase (LDH)
 
• Potassium
 
• Sodium
 
• Total Bilirubin
 
• Total Protein
 
	
 
• Hematocrit
 
• Hemoglobin
 
• Mean Corpuscular Hemoglobin Concentration (MCHC)
 
• Mean Corpuscular Volume (MCV)
 
• Platelet Count
 
• Red Blood Cell Count (RBC)
 
• White Blood Cell Count (WBC) with Differential (Absolute) 
 
○ Bands
 
○ Blasts
 
○ Basophils
 
○ Eosinophils
 
○ Lymphocytes
 
○ Monocytes
 
○ Neutrophils
 
 
 

Serum chemistry and hematology summaries will present scheduled visit and include baseline (Screening, Baseline, W1 Safety Assessment, W2 Safety Assessment, EOS 1 Week Post-excision, EOS 2 Weeks Post-excision) within alphabetically ordered laboratory parameters and, for continuous parameters, include descriptive statistics for baseline and change from baseline for post-baseline visits, if possible.

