The serum tryptase summary will present scheduled visit and include baseline (Screening, Baseline, W1D1, W1D2, W1D3, W2D1, W2D2, W2D3 – not all labs are collected at all scheduled visits) and include descriptive statistics for baseline and change from baseline for post-baseline visits without timepoints, if possible. If timepoint measurements occur, serum tryptase will be displayed by scheduled timepoint (Immediately after Hypersensitivity Reaction, 60-120 min after Hypersensitivity Reaction) within scheduled post-baseline visit and include (a) descriptive statistics for

baseline and change from baseline for post-baseline timepoints, if possible, and (b) the number and percent of subjects with at least one significant elevation, where significant elevation of serum tryptase is defined as a post-baseline value  $\geq (1.2 \times \text{baseline value}) + 2$ .

Shift tables for laboratory parameters previously listed in this section of the SAP for (a) serum chemistry and (b) hematology will be presented, if possible, at each scheduled post-baseline visit using the safety population. Abnormal/out of range laboratory values are to be flagged as either Low or High. As CTCAE grading is not provided for numerous laboratory data, shift tables to assess changes from baseline will be presented using Low, Normal, High, and Total as categories.

Separate listing will be provided for serum chemistry, hematology, and serum tryptase using the safety population, and these lab listings will include whether Collection was Performed (Yes, No), Visit, Date and Time of Collection, Result and Units using the International System of Units (i.e., standard units), Lower and Upper Reference Range Limits using the International System of Units, Reference Range Indicator (Low, Normal, High), if available, CTCAE grade, if available, Clinical Significance (NCS, CS) for abnormal results, if available, and Change from Baseline using the International System of Units. The serum tryptase listing will also include the following for post-baseline results:

- Did the subject have a hypersensitivity reaction?
- Was a blood sample collected immediately after the hypersensitivity reaction for the serum tryptase assessment collected?
- Was the second blood sample collected between 60 - 120 minutes after the hypersensitivity reaction for the serum tryptase assessment collected?

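### Post-baseline chemistry and hematology tables omit Unscheduled Visit results and keep only the last of several same-visit readings, with no worst-value display, so shifts to abnormal can be under-counted

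*SAP*

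**What the plan says.** Two general rules in SAP section 5.2 decide which readings reach a table. The first concerns visits: "Tables will be summarized for scheduled visits unless stated otherwise in this SAP". The second concerns several readings within one visit: "If there are multiple readings taken per visit, the most recent reading from that visit will be used in summaries". That second rule has one exception: "unless there are pre-dose and post-dose readings taken at the same visit, as mentioned elsewhere in this SAP".

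SAP section 9.2 applies these rules to the laboratory panels. The descriptive summaries of chemistry and hematology name Screening, Baseline, the two weekly Safety Assessments and the two end-of-study visits. The shift tables use Low, Normal, High and Total as categories and "will be presented, if possible, at each scheduled post-baseline visit using the safety population". Neither display has a row for an Unscheduled Visit or for the worst post-baseline value.

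The protocol does produce results outside those visits. Under section 8.4.4 the tests "will be performed at Screening, at each Safety Assessment Visit, at Unscheduled Visits and at the EOS", and footnote g to the Schedule of Assessments says the same.

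**The concern.** A shift table should show how many subjects moved from a normal baseline to an abnormal value on treatment. Here two kinds of post-baseline reading cannot contribute: anything drawn at an Unscheduled Visit, and any earlier reading when more than one is recorded under the same scheduled visit. If repeat draws are made mainly because the first result was abnormal, the second rule tends to replace abnormal values with values closer to normal.

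The adverse-event tables only partly make up for this. SAP section 9.2 sends clinically significant post-baseline results there. Protocol section 10.1.2, however, says that abnormal findings without clinical significance should generally not be recorded as adverse events. An excluded Low or High value of that kind therefore reaches no summary table. At stake is the completeness of the planned tabulation of Low and High results in a study whose primary objective is safety and tolerability (protocol section 11.2). SAP section 14 replaces toxicity-grade shifts with Low/Normal/High shifts, so no graded laboratory shift table is planned that might pick these values up.

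**Working it through.** The documents state no figure on this point. The check has two parts: tracing what happens to a reading under the rules, and an illustrative calculation for the one case in which a value is replaced.

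**Tracing by case** (SAP sections 5.2, 5.5 and 9.2 against protocol sections 8.4.4 and 10.1.2)

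1. *Post-baseline chemistry or hematology value at an Unscheduled Visit.* It is absent from the descriptive and shift tables. It falls within the scope of the by-subject listing, and it is in the adverse-event tables if clinically significant.
2. *Abnormal value at a scheduled visit, normal retest at an Unscheduled Visit.* The abnormal value stays in the table and the retest is left out. Nothing is overwritten.
3. *Abnormal value and normal repeat recorded under the same scheduled visit.* The repeat replaces the abnormal value in the table. Both readings fall within the scope of the listing.
4. *Serum tryptase after a hypersensitivity reaction.* SAP section 9.2 shows the immediate and the 60-120 minute readings separately and counts every subject with a significant elevation. Nothing is lost.
5. *Unscheduled value before the first injection.* It can enter the tables as baseline, because SAP section 5.5 takes the latest non-missing value before the first injection and does not limit it to scheduled visits.

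The gap is therefore cases 1 and 3, for chemistry and hematology. The pre-/post-dose exception does not close it, because the Schedule of Assessments does not place these panels at the treatment visits.

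**Size of case 3**

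All inputs are assumptions, since the documents give neither a repeat rate nor a within-person correlation:

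- the two readings Z1 and Z2 are standard bivariate normal with correlation ρ of 0.6, 0.8 or 0.9;
- abnormal means above the 97.5% limit, so Z > 1.96 and P(Z1 > 1.96) = 0.025;
- r is the share of abnormal first results that are repeated under the same scheduled visit.

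Formulas:

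P(repeat abnormal | first abnormal) = P(Z1 > 1.96 and Z2 > 1.96) / 0.025

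Share of abnormal first results lost from the table = r × [1 − P(repeat abnormal | first abnormal)]

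| ρ | Joint probability | Repeat abnormal again | Lost if r = 100% | r = 25% | r = 10% | r = 5% |
|---|---|---|---|---|---|---|
| 0.6 | 0.00622 | 0.249 | 75% | 19% | 7.5% | 3.8% |
| 0.8 | 0.01097 | 0.439 | 56% | 14% | 5.6% | 2.8% |
| 0.9 | 0.01482 | 0.593 | 41% | 10% | 4.1% | 2.0% |

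For ρ = 0.6 and r = 10%: 0.00622 / 0.025 = 0.249; 1 − 0.249 = 0.751; 0.10 × 0.751 = 7.5%.

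These are losses among abnormal first results only. The last-reading rule itself has no direction. In this model Z1 and Z2 have the same distribution, so if repeats were made regardless of the first result, normal values replaced by abnormal ones would on average balance the losses. The tilt towards normal arises only if abnormal first results are repeated more often than normal ones.

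**Size of case 1.** All post-baseline Unscheduled Visit results are left out of these tables, but the documents give no basis for estimating how many there will be.

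**The case against.** The strongest reply is that no data are lost. SAP section 5.2 provides listings of the collected data without restricting them to scheduled visits. Section 9.2 lists all three panels by subject, with visit, date and time, range flag, clinical significance where available, and change from baseline. Clinically significant results go to the adverse-event tables, and protocol section 10.1.2 also treats laboratory changes that require therapy as adverse events. What is missing from every table is limited to post-baseline abnormalities judged not clinically significant, in a descriptive study whose list of safety endpoints tied to objectives (protocol section 11.4.1) does not include laboratory values. All of this stands, and it makes the point a modest one. It does not remove it, because a listing gives no count or percentage.

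A reader might also infer that values from Unscheduled Visits never appear anywhere, or that a normal retest generally overwrites the abnormal result that prompted it. The documents support neither. Listings and adverse-event tables carry such values, and a retest at an Unscheduled Visit leaves the abnormal scheduled value in place, so for that retest the scheduled-visit rule keeps the abnormal result. The protocol describes no same-visit repeat of chemistry or hematology; the extra occasion that it does provide is the Unscheduled Visit. Nor do the documents say that unscheduled draws or repeats are prompted by abnormal results. That is plausible, but it is an assumption.

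It would likewise be wrong to read 41-75% as the expected loss. That range holds only if every abnormal result is repeated under the same visit.

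**Conclusion.** The concern holds as a limited gap. Post-baseline chemistry and hematology tables leave out Unscheduled Visit results, keep only the last of several readings under one scheduled visit, and have no worst-value display to compensate. Abnormal values excluded in this way and not judged clinically significant are visible only in listings, so the shift tables can under-count shifts to abnormal. Whether they will do so to a material degree cannot be settled from the documents. The loss from same-visit repeats scales directly with an unknown repeat rate (about 2-4% at 5%, 4-8% at 10%, 10-19% at 25%), and the number of unscheduled draws is also unknown. A claim of systematic under-reporting would go beyond this evidence. The point is worth acting on because the remedy is cheap and uses data already collected. The SAP already counts any significant tryptase elevation (section 9.2) and uses unscheduled treatment visits for necrosis (section 7.1.2), so the approach is not foreign to it.

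**What to change.** In SAP section 9.2, add for each serum chemistry and hematology parameter a shift from baseline to the worst post-baseline value, once for the lowest and once for the highest. State that it uses all post-baseline results, including Unscheduled Visits and repeat draws within a visit. Keep the by-visit summaries and shift tables as planned. With the worst-value shift in place, the within-visit rule no longer decides whether an abnormal value is counted, so it need not change.

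The cost is one extra table per panel, some SAP wording and slightly less favourable abnormal counts. No new data are needed, since values, dates and, where available, range flags are already planned for the listings. The change should be made before database lock, because SAP section 5.2 labels anything added later as post hoc.

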### **5.3. Multiplicity/Multiple Comparisons**

There are no inferential statistical analyses planned for this study, and therefore, there are no multiplicity concerns.

### **5.4. Covariate Adjustments and Multicenter Analysis**

No covariate analyses will be performed. No multicenter analyses will be performed.

### **5.5. Definition of Baseline and Treatment Groups**

Baseline is defined as the most recent non-missing value obtained prior to first injection of study treatment. Summaries will be provided for the following groups, unless limited to a subset of these groups elsewhere in this SAP:

- Part 1
- Part 2
  - Cohort 1
  - Cohort 2
  - Cohort 4
  - Cohort 4 Expansion
  - Cohort 5
  - Cohort 5 Expansion
  - Overall (i.e., Part 2 Total, Displayed Total, or Expansion Total)

No other group or subgroup analyses will be performed.

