### **3.6. Cohort 4 (N = 36 [10 initial / 26 expansion] at two times weekly dosing)**

Subjects receive VP-315 via once-daily dosing of 8 mg, administered on 2 consecutive days in one week (W1D1, W1D2). The planned dosing regimen is a split dose of VP-315 for all treatments. The 500 $\mu$ L (8 mg) dose is to be divided into 2 injections given at least 15 minutes and no more than 30 minutes apart, with 30% (150  $\mu$ L) administered in the first injection and the remaining 70% (350  $\mu$ L) with the second injection. Treatment for a second TL may begin on D1 of the next week (W2D1, W2D2). Each individual TL is treated for the assigned 2 days only (regardless of necrosis status). Up to 2 TLs may be treated – up to 4 total doses. Subjects with only 1 TL who complete week one of treatment without complete necrosis receive no additional treatment.

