### **3.7. Cohort 5 (N = 37 [10 initial / 27 expansion] at three times weekly dosing)**

Subjects receive VP-315 via once-daily dosing of 8 mg, administered on 3 consecutive days in one week (W1D1, W1D2, W1D3). The planned dosing regimen is a split dose of VP-315 for all treatments. The 500 $\mu$ L (8 mg) dose is to be divided into 2 injections given at least 15 minutes and no more than 30 minutes apart, with 30% (150  $\mu$ L) administered in the first injection and the remaining 70% (350  $\mu$ L) with the second injection. Treatment for a second TL may begin on D1 of the next week (W2D1, W2D2, W2D3). Each individual TL is treated for the assigned 3 days only (regardless of necrosis status). Up to 2 TLs may be treated – up to 6 total doses. Subjects with only 1 TL who complete week one of treatment without complete necrosis receive no additional treatment.

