## **6. Analysis Populations**

**Enrolled Subjects:** Enrolled subjects are subjects who signed the informed consent form and were not screen failed. Enrolled subjects will serve as the population for certain analyses as described in this SAP.

**Safety (SAF) Population:** The Safety Population will include all subjects who received at least one injection of VP-315. The SAF Population will serve as the primary population for the analysis of safety-related data.

**Full Analysis (FA) Population:** The Full Analysis Population will include enrolled subjects who received one full dose (actual equals expected for at least one treated lesion) of VP-315 (for Part 1 and Part 2 Cohorts 4 and 5, a full dose consists of two injections) and have at least one non-missing post-baseline efficacy observation for histologic clearance of lesions at excision (see Section 8 of this SAP for details). The FA Population will serve as the primary population for the analysis of efficacy-related data.

**Per-protocol (PP) Population:** The Per-protocol Population will include FA subjects who have no major protocol deviations that may substantially affect the results of the efficacy analyses outlined in Section 8 of this SAP. The final determination on protocol violations, and thereby the composition of the PP, will be made before database lock.

The PP Population will be used as the secondary population for the efficacy analyses outlined in Section 8 of this SAP.

A non-exhaustive list of potential major protocol deviations is provided below:

- Investigational Product Deviations
  - Subject received wrong treatment
  - Deviation in IP storage
  - Error in IP dosing
- Enrollment Deviations
  - Subject is enrolled prior to determining whether eligible for study
  - Ineligible subject is enrolled
  - Enrollment occurs outside protocol window
- Study Data and/or Forms Deviations
  - Forms or data not sent from clinical site to coordinating center
  - Missing data and/or form
  - Missing images and/or operative reports
- Subject Deviations
  - Subject administration of a prohibited medication
  - Subject compliance with protocol
  - Subject met withdrawal criteria but was not withdrawn
- Visit/Procedure Schedule Deviations
  - Visit/Procedure not completed
  - Visit/Procedure not completed in window

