### 7.1.1. Subject Disposition

A summary of subject disposition will be provided using enrolled subjects. The number and percentage of subjects who were enrolled, completed the study, and are included in the Safety, Full Analysis, Per Protocol, and PK Populations will be summarized, along with the reason for exclusion from the Safety, Full Analysis, Per Protocol, and PK Populations. The number and percentage of subjects discontinuing from study, and the primary reason for discontinuation from study, will also be included in the summary.

Separate listings will be provided for the following using all subjects including screen failures:

- Informed Consent (Was Subject Reconsented (Yes, No), Date of Consent/Reconsent, Date of Advarra ICF IRB Approved Version, Protocol Version Number, Version of Consent Signed (Part 1)),
- Inclusion/Exclusion (Subject Enrolled in Study (Yes, No), Enrollment Date, Part (Part 1, Part 2), Cohort (Cohort 1, Cohort 2, Cohort 4, Cohort 4 Expansion, Cohort 5, Cohort 5 Expansion), Subject Current Screen Failure (Yes, No), Subject Previous Screen Failure (Yes, No), Previous Subject ID, category/label and text for each Inclusion Criterion Not Met and each Exclusion Criterion Met for current or previous screen failure, Screen Fail Reason for current or previous screen failure), and
- Subject Visits (Visit, Date of Visit, whether Not Done, and Reason Not Done).

Separate listings will be provided for the following using enrolled subjects:

- Analysis Populations (Yes/No for Subject Inclusion in Each Population),
- End of Treatment Surgical Excision (Date Assessment Performed, All Lesions Surgically Excised (Yes, No) with Specified Reason, if applicable, Other Assessments Performed (Yes, No) with Specified Assessments, if applicable),
- End of Study Suture Removal and Post-surgical Assessment (Visit, Sutures Removed (Yes, No), Post-surgical Assessment Performed (Yes, No), Date Assessment Performed, Clinically Significant Findings (Yes, No)),

- Follow-up Call (Date of Visit, Ongoing Adverse Event Since End of Study (Yes, No), Subject Died Since Last Visit (Yes, No), Date of Death, Cause of Death (Adverse Event, Other)), and
- Subject Disposition (Enrollment Date, Date of Last Dose of Study Treatment, Date of Discontinuation or Completion of Study, Study Treatment Discontinuation and Study Discontinuation Statuses and Reasons, Date of Last Contact, and Date and Cause of Death).

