### **8.3. Estimate of Remaining Tumor Volume and Reduction in Tumor Volume at Excision**

Protocol endpoints reference that the estimated remaining tumor volume would be necrotic cells:tumor cells. However, estimated remaining tumor volume is the estimated volume of residual viable tumor cells. The assessment in the EDC is expressed as a percentage of viable tumor cells within the tumor bed which is composed of tumor cells (viable and necrotic), fibrosis, and inflammation.

A summary of the estimated remaining tumor volume (0 = None Remaining to 100 = All Remaining) will be provided using descriptive statistics for excised lesions (TL1, TL2, NTL1, NTL2, NTL3) from the end-of-treatment (EOT) visit. A 95% confidence interval for the mean estimated remaining tumor volume will also be provided in the summary using a one sample, two-sided t-test. Summary measures will be repeated for reduction in tumor volume (0 = No reduction to 100 = None Remaining).

The summaries will use the full analysis population, and for each lesion, descriptive statistics will be provided in the summary. The summaries will also be run using the per-protocol population as outlined in Section 6 of this SAP.

A separate listing will be provided for the excision of all lesions as described in Section 8.1 of this SAP.

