## 8.6. Complete Clearance of Treated Lesions at Excision

Complete clearance occurs when histologic clearance, as defined in Section 8.1 of this SAP, and clinical clearance, as defined in Section 8.2 of this SAP, are both achieved.

A summary of complete clearance will be provided using histologic clearance and clinical clearance of excised treated lesions (TL1, TL2) from the end-of-treatment (EOT) visit. The clearance categories are as follows:

- Histologic Clearance (i.e., Scar) and Clinical Clearance (i.e., 100% Improvement, No Visible Tumor)
- Histologic Clearance and Not Clinical Clearance
- Not Histologic Clearance and Clinical Clearance
- Not Histologic Clearance and Not Clinical Clearance

The summary will use the full analysis population, and for each treated lesion, the number and percentage of subjects falling into each clearance category will be provided in the summary. The summary will also be run using the per-protocol population as outlined in Section 6 of this SAP.

A separate listing will be provided for the excision of all lesions as described in Section 8.1 of this SAP, and a separate listing will be provided for the PGA of all lesions as described in Section 8.2 of this SAP.

Part 2 Cohort 4, Cohort 4 Expansion, Cohort 5, Cohort 5 Expansion, and overall (Cohorts 4 and 5 and Expansion Cohorts 4 and 5, i.e., Displayed Total) will be summarized in one display; Part 1, all Part 2 cohorts, and overall (Part 2 Total) will be summarized in another display.

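### No planned efficacy or safety column holds all subjects on the 2-day regimen (Cohort 4, 36) or the 3-day regimen (Cohort 5, 37); every pooled column mixes the regimens

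*SAP*

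**What the plan says.** SAP 5.5 sets the columns for all tables unless a later section narrows them: Part 1; then, within Part 2, Cohort 1, Cohort 2, Cohort 4, Cohort 4 Expansion, Cohort 5 and Cohort 5 Expansion; and a final entry, "Overall (i.e., Part 2 Total, Displayed Total, or Expansion Total". The section ends with "No other group or subgroup analyses will be performed". SAP 8 (efficacy) and SAP 9 (safety) apply the Section 5 conventions and add no column per regimen.

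The label Cohort 4 is used in two ways.

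- The headings of SAP 3.6 and 3.7 use it for everyone on the regimen: "Cohort 4 (N = 36 [10 initial / 26 expansion] at two times weekly dosing" and "Cohort 5 (N = 37 [10 initial / 27 expansion] at three times weekly dosing".
- SAP 7.1.1 lists the labels as alternative values of one field: "Cohort (Cohort 1, Cohort 2, Cohort 4, Cohort 4 Expansion, Cohort 5, Cohort 5 Expansion". SAP 8.6 builds its pooled column by naming both kinds of group: "overall (Cohorts 4 and 5 and Expansion Cohorts 4 and 5, i.e., Displayed Total) will be summarized in one display".

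SAP 5.5 does not say which meaning applies to its columns.

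The only confidence interval in the SAP is in 8.3: "A 95% confidence interval for the mean estimated remaining tumor volume will also be provided in the summary". Histologic, clinical and complete clearance (SAP 8.1, 8.2, 8.6) get counts and percentages only.

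**The concern.** Within Cohort 4 the initial and expansion subjects receive the same daily dose on the same 2-day schedule. Within Cohort 5 both receive it on the same 3-day schedule. The number of dosing days per lesion is the planned contrast between the cohorts. The primary objective for Cohorts 4 and 5 (Protocol 3) is to learn more about safety, tolerability and dosing regimen for the design of a pivotal study, and Protocol 2.3.2 speaks of an optimal regimen determined from these two cohorts.

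As planned, each regimen is reported as one fragment of 10 subjects and one of 26 or 27. The only larger columns blend the two regimens. The team designing the next study would have no planned estimate of clearance, treatment-related events or cutaneous reactions for either regimen as a whole. Under SAP 5.2, an analysis added after database lock is labelled post hoc.

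**Working it through.** **1. Group sizes (SAP 3.2 to 3.7).** The stated figures reproduce: 10 + 26 = 36; 10 + 27 = 37; 6 + 3 + 36 + 37 = 82.

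**2. What each Part 2 column holds.**

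| Column | 2-day | 3-day | Other | Total |
|---|---|---|---|---|
| Cohort 1 | – | – | 6 | 6 |
| Cohort 2 | – | – | 3 | 3 |
| Cohort 4 | 10 | – | – | 10 |
| Cohort 4 Expansion | 26 | – | – | 26 |
| Cohort 5 | – | 10 | – | 10 |
| Cohort 5 Expansion | – | 27 | – | 27 |
| Expansion Total | 26 | 27 | – | 53 |
| Displayed Total | 36 | 37 | – | 73 |
| Part 2 Total | 36 | 37 | 9 | 82 |

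No column equals 36 two-day or 37 three-day subjects. The Displayed Total is 36/73 = 49.3% two-day and 37/73 = 50.7% three-day. The 9 subjects added in the Part 2 Total are on two further regimens.

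**3. The other reading of the label.** Suppose the Cohort 4 and Cohort 5 columns meant all 36 and all 37. The Displayed Total in SAP 8.6 would then name the expansion subjects twice; taken as a sum it would be 36 + 37 + 26 + 27 = 126, more than the 82 subjects in Part 2. The single cohort field in SAP 7.1.1 could not hold both labels for one subject either. The columns therefore mean the 10 initial subjects each.

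**4. Precision.** The documents give no clearance rate, so about 50% is assumed for illustration. The exact (Clopper-Pearson) 95% limits for x of n are the 0.025 quantile of Beta(x, n − x + 1) and the 0.975 quantile of Beta(x + 1, n − x). For an event not seen, the two-sided 95% upper limit is 1 − 0.025^(1/n). The half-width of the SAP 8.3 interval for mean tumour volume is t(0.975, n − 1)/√n in SD units, with full data and one lesion per subject.

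| n | x | Exact 95% CI | Upper limit, 0 events | t half-width (SD) |
|---|---|---|---|---|
| 10 | 5 | 18.7–81.3% | 30.8% | 0.72 |
| 26 | 13 | 29.9–70.1% | 13.2% | 0.40 |
| **36** | 18 | **32.9–67.1%** | **9.7%** | **0.34** |
| 27 | 14 | 31.9–71.3% | 12.8% | 0.40 |
| **37** | 18 | **31.9–65.6%** | **9.5%** | **0.33** |

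The Full Analysis Population may be smaller, since SAP 6 requires a full dose and that subjects "have at least one non-missing post-baseline efficacy observation for histologic clearance of lesions at excision". Assumed denominators of 34, 30 and 28 give 32.4–67.6% (17/34), 31.3–68.7% (15/30) and 30.6–69.4% (14/28).

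**5. What can be rebuilt from the split columns.** Counts add. With n = n₁ + n₂, the pooled mean is (n₁m₁ + n₂m₂)/n and the pooled variance is [(n₁ − 1)s₁² + (n₂ − 1)s₂² + (n₁n₂/n)(m₁ − m₂)²]/(n − 1). On simulated groups of 10 and 26 this reproduced the pooled mean and SD exactly. Medians cannot be combined from the columns.

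**6. Monitoring time.** Initial subjects were monitored for up to 2 hours after the second injection. Expansion subjects were monitored for up to 1 hour, extendable by the investigator (Protocol 4.1, 8.4.2). In a pooled safety column, 10/36 = 27.8% and 10/37 = 27.0% of subjects are those planned for the longer window, while SAP 9.3 lists blood pressure timepoints out to 120 minutes.

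**The case against.** The strongest reply is that almost nothing is lost. The primary endpoints for these cohorts and all three clearance endpoints are counts in columns that do not overlap, so a regimen total is one addition. The tumour volume mean, SD and t interval can be pooled by formula. Even the tumour volume median can be rebuilt, because the excision listing in SAP 8.1 gives each lesion's value and the SAP 7.1.1 listing gives each subject's cohort. SAP 5.2 allows later analyses if they are labelled post hoc, and SAP 15 allows minor changes in display categories. Protocol 11.1, 11.5.2 and 11.5.3 promised analysis by study part only, so the SAP already gives more. Protocol 4.1 and the synopsis also describe Cohorts 4 and 5 as receiving a regimen already chosen, which weakens the case that they serve to select one. Separate columns have a real basis too: a safety committee review came between the groups, and monitoring time differed.

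This limits the impact, and the split columns should stay. It does not supply the missing estimate. Rebuilding by hand or from listings is the reader's analysis, not the plan's, and SAP 5.5 closes the list in plain terms. Whatever was chosen earlier, the cohorts still differ in 2 against 3 dosing days, and the stated objective includes the regimen.

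Two further points are fair. The absence of clearance intervals is a separate choice that regimen columns alone would not cure. And SAP 9.1 counts special-interest events on any treatment day in both groups, so the monitoring caveat concerns how likely an event is to be detected, not how it is defined.

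**Conclusion.** The concern holds. On the better reading of SAP 5.5, with 7.1.1 and 8.6, the plan has no efficacy or safety column for the 36 subjects on the 2-day regimen or the 37 on the 3-day regimen, and each available total mixes regimens, roughly half and half in the Displayed Total. The label itself is undefined, which is a defect on either reading.

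For a whole regimen, the exact interval at an assumed 50% clearance narrows from 19–81% (n = 10) or 30–70% (n = 26) to about 33–67% (n = 36). The upper limit for an unseen event falls from 31% or 13% to 10%. These figures rest on the assumed rate and on complete denominators. They show what a regimen column would offer; they do not measure an error in any planned number. Cohorts 1 and 2 and the PK tables already have one column per regimen and are not affected. The change should be made, but the study's data and conduct do not depend on it.

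**What to change.** In SAP 5.5:

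- State that the Cohort 4 and Cohort 5 columns are the 10 initial subjects each, and keep them and the expansion columns.
- Add Cohort 4 Total (2-day) and Cohort 5 Total (3-day) columns to the efficacy, treatment-related event, special-interest event and cutaneous reaction tables, and amend the closing sentence to match.
- Give an exact 95% interval for histologic, clinical and complete clearance of the first target lesion (TL1) per regimen, on the actual Full Analysis denominators.
- Footnote that allocation to the cohorts was sequential, and that post-dose monitoring was up to 2 hours for initial subjects and up to 1 hour, extendable by the investigator, for expansion subjects, so pooled hypotension and special-interest counts mix ascertainment windows.

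A descriptive difference between regimens is optional. The cost is SAP wording, two columns, the clearance intervals and one footnote, with no new data. The estimates remain descriptive and non-randomised. If the database is already locked, the columns can still be produced but must carry the post hoc label that SAP 5.2 requires.
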